Also missing from this literature is delivery of activity-focused interventions of any kind to individuals with PD in low SES communities. An unpublished zip code based demographic analysis of the 114 participants in a recently completed NIH R01 funded study on effective exercise approaches for individuals with PD found participants in the study resided in communities with only 31.3% of the households earned less than \$25,000 per year and 26.2% of the population earned more than \$100,000 per year. These percentages are vastly different than the 39.6% of the MO population that earns less than \$25,000 and 13.3% that earns over \$100,000. For individuals in lower SES communities, access to exercise programs is lacking.

The two studies described here seek to address the above highlighted problems in intervention implementation for individuals with PD in underserved communities. We will examine the effectiveness, feasibility, and ideal methodological approach for delivery of an in-home exercise program. This intervention will allow the individuals enrolled to participate in regular exercise and a community activity that promotes social support and engagement. Additionally, we will compare a solo versus partnered protocol to examine the possible benefits of partnered, socially supported exercise.

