## Specific Aims

### **Study 1**

**SPECIFIC AIM 1:** Examine the reach and maintenance of an in-home cycling program for underserved individuals with PD. Reach will be assessed by examining the demographic characteristics of the individuals enrolled and through the administration of a questionnaire on objective and subjective socioeconomic status to better understand their level of accessibility to services, perceived barriers and economic status. We will also explore the implementation of a health coach to promote effective maintenance of the program after the 6-month intervention. Finally, we will conduct two interviews to better understand strengths and weakness of the program and to better address the needs of the participants in future studies.

**Hypothesis 1a:** Demographic characteristics including race and socioeconomic status of the enrolled participants will not statistically differ from the characteristics of the state of WI.

**Hypothesis 1b:** Feedback from participant interviews will inform future delivery of the in-home cycling program.

**SPECIFIC AIM 2:** Determine the effectiveness of a 6-month in-home, progressive, tele-exercise cycling program and 3-month health coach follow-up for underserved populations of individuals with PD.

**Hypothesis 2a:** Participants will improve performance of activities of daily living from baseline to posttest. These effects will be maintained at 3-month follow-up.

**Hypothesis 2b:** Participants will significantly improve measures of gait and balance performance and non-significantly improve fall rate from baseline to posttest. These effects will be maintained at 3-month follow-up in the group piloting implementation of a health coach, but not in solo follow-up group. Falls data will allow for effect size calculations for future applications.

**Hypothesis 2c:** Activity level as measured by an activity monitor will increase from baseline to posttest. This effect will be maintained at 3-month follow-up in health coach group, but not in the solo group.

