### **Study 2**

**SPECIFIC AIM 1:** Determine whether incorporation of social interaction during physical activity significantly improves task adherence and increases task stamina as compared to solo cycling.

**Hypothesis 1a:** Those individuals participating in socially engaged cycling will complete a significantly greater number of cycling sessions than individuals in the solo cycling group.

**Hypothesis 1b:** Individuals in the social cycling group will cycle for longer durations at each session than solo cyclists, despite the long term goal being 30 minutes per session for both groups.

**SPECIFIC AIM 2:** Determine whether incorporation of social interaction during physical activity significantly improves activities of daily living, fall rate and quantity of movement for individuals with PD. The primary variables for this aim are Performance Assessment of Self-care Skills Assessment scores, gait velocity and step count.

**Hypothesis 2a:** Socially engaged exercise will result in significantly greater improvement in measures of instrumented activities of daily living (IADL; as measured by the Performance Assessment of Self-care Skills (PASS) assessment) as compared to solo cycling.

**Hypothesis 2b:** Fall rate will be non-significantly improved with socially engaged cycling but not with solo cycling. Weekly calls will be placed to both groups to record fall rate. Falls data will allow for effect size calculations for future applications.

**Hypothesis 2c:** Overall activity level, as measured by an activity monitor, will increase with socially engaged cycling but not with solo cycling.

**Study Duration:** This study will be conducted over the next 4 years including all data analysis, manuscript and grant proposal submissions.

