### **Research Design**

This pilot study will utilize two separate experimental designs to address: 1) the Reach, Effectiveness, Implementation and Maintenance and 2) the optimal delivery method for an in-home exercise intervention program for individuals with PD living in underserved communities. Both studies will utilize paired, randomly assigned groups to explore the given questions. Pairs will be based on disease severity (UPDRS III scores) and age.

Study 1: The proposed pilot study will utilize the RE-AIM framework (Reach, Effectiveness, Adoption, Implementation and Maintenance) to focus on the reach and effectiveness of a 6-month triweekly in-home cycling program and then pilot a health coach model to promote maintenance for the subsequent 3-month period. 40 qualified individuals will be paired based on disease severity (score on subsection III of the UPDRS) and age and randomly assigned to either the cycling group or the normal care control group for 6 months. For those in the cycling group, participants will interact via Skype with study team members during all cycling sessions. This intervention will allow the individuals enrolled to participate in regular exercise and a community activity that promotes social support and engagement. The proposed pilot maintenance model for the 3-month period following the intervention will implement a health coach model with scheduled sessions every other week to discuss goals and motivation while decreasing the total contact time with the participant. Individuals in the normal care control group will crossover and complete the cycling intervention following the initial 6 months.

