## Power and Statistical Analysis

As this is a pilot study, we have not proposed a recruitment level that will properly power the outcome measures for a desired effect size. Previous work by [name] during her post-doctoral training under the guidance of [name] at Washington University in St. Louis indicate that approximately 27 individuals per group are needed to provide 89% power to detect differences in a similar intervention at a significance level of 0.05. This estimate uses gait velocity as the primary variable of interest and relies on a previous measured average forward gait velocity of  $1.2 \pm 0.1 \text{ m/s}$  and an average backward gait velocity of  $0.6 \pm 0.1 \text{ m/s}$  for 60 individuals with PD. The estimate is designed to detect a difference of 1 SD or  $0.1 \text{ m/s}$ , which is equivalent to an effect size of 0.4. Additionally, an attrition rate of approximately 15-20% should be expected. As the future RCT will likely focus on spatiotemporal measures collected during ADL task performance, this estimate provides some guidance for future work, but ideally future proposals will be powered from pilot data on the aims proposed herein. The proposed study of 40 individuals (20 per group) will provide pilot data which will be used to estimate effect size for the subsequent proposal (study 1).

To examine the reach of the project into the lower SES Parkinson disease community, we will analyze questions 6 and 7 of the MacArthur Scale of Subjective Social Status. A descriptive analysis of these data and subsequent comparison to income data for the state of WI will allow us to assess if individuals with PD in lower SES communities were optimally targeted.

To examine the qualitative effectiveness of the cycling intervention as well as the health coach intervention we will code the responses from the survey, assess common themes and use these data to inform the development of a larger RCT.

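### Study 1 Hypothesis 1a takes the absence of a significant difference from Wisconsin as evidence of reach, with 40 participants and no margin, and the descriptive reach analysis does not match it

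*Combined protocol and SAP*

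**What the plan says.** Specific Aims, Study 1, Aim 1 is about reach and maintenance. It says "Reach will be assessed by examining the demographic characteristics of the individuals enrolled", together with a questionnaire on objective and subjective socioeconomic status. Hypothesis 1a then predicts that demographic characteristics, race and socioeconomic status among them, "will not statistically differ from the characteristics of the state of WI".

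Research Design sets the Study 1 sample: "40 qualified individuals will be paired based on disease severity" and age. Power and Statistical Analysis repeats the figure of 40 (20 per group) and says that this pilot is not sized to power its outcome measures.

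The same section holds the only reach analysis: "we will analyze questions 6 and 7 of the MacArthur Scale of Subjective Social Status". The method is "A descriptive analysis of these data and subsequent comparison to income data for the state of WI", and the stated purpose is to judge whether lower-SES communities were well targeted. No test, significance level or margin is named for reach, and race is not mentioned. The repeated-measures ANOVA paragraph lists no reach variable. The Baseline assessment does collect demographic data.

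**The concern.** The hypothesis makes a null result its success criterion. Without a margin, such a criterion becomes easier to meet as the sample shrinks, because a smaller study detects fewer real differences. Reach is a stated aim of Study 1, and representation of underserved people is the reason for the project. If the report follows the wording of Hypothesis 1a, a sample with too few low-income participants, or with nobody from a smaller racial group, could be described as consistent with the state.

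The hypothesis and the analysis section also differ on three points:

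- **Method:** statistical difference in one, description in the other.
- **Variables:** race and socioeconomic status in one, two questionnaire items compared with income data in the other.
- **Criterion:** matching the state in one, successful targeting of lower-SES communities in the other.

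The plan therefore does not say which of the two will govern the reported conclusion.

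**Working it through.** The plan states no sample size, power or margin for Hypothesis 1a, so there is no figure of its own to reproduce. The calculations below show what the hypothesis would tolerate if a test were applied.

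**Inputs**

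- n = 40 enrolled (Research Design). The 15–20% attrition figure is not applied, because reach concerns those enrolled.
- Two-sided alpha of 0.05. This is an assumption: the plan gives 0.05 only for its gait-velocity estimate.
- Income illustration from Background and Significance: a low-income share of 31.3% in the communities of an earlier study's participants against 39.6% for Missouri, and a high-income share of 26.2% against 13.3%. The Background says of the two contrasts together: "These percentages are vastly different than the 39.6% of the MO population that earns less than" the low-income threshold. These are zip-code community shares for another state. Treating them as individual probabilities is an assumption.
- Wisconsin income and race shares are not in the documents, so ranges are assumed.

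**Test.** One-sample exact binomial. The two-sided p-value for count x is the sum of P(X = k | n, p0) over all k that are no more probable than x.

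**Low income, p0 = 39.6%**

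- p = 0.034 at 9, 0.074 at 10, 0.053 at 22 and 0.024 at 23. Every count from 10 to 22 (25% to 55%) is therefore non-significant.
- If the true share is 31.3%, P(10 ≤ X ≤ 22) = 0.848. The gap of 39.6 − 31.3 = 8.3 points is missed about 85% of the time.

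**High income, p0 = 13.3%**

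- Counts 1 to 9 are non-significant. If the true share is 26.2%, the gap is missed 37% of the time.

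**Both contrasts together.** The true shares (low, high, middle) are 0.313, 0.262 and 1 − 0.313 − 0.262 = 0.425. The reference shares are 0.396, 0.133 and 0.471.

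- Both exact tests non-significant: probability 0.346.
- Three-category chi-square (2 df) non-significant: probability 0.453.

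The full skew is missed 35% to 45% of the time.

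**Sensitivity to the assumed state share.** An 8.3-point shortfall at n = 40:

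| Assumed low-income share | Missed |
|---|---|
| 20% | 70% |
| 25% | 82% |
| 30% | 80% |
| 35% | 78% |
| 39.6% | 85% |
| 45% | 85% |

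**Race.** For zero enrolled, P(X = 0) = (1 − p0)^40. At p0 = 8.3% this is 0.917^40 = 0.031, and the two-sided p is 0.076. At 8.4% the two-sided p is 0.047, and at 10% it is 0.030. Enrolling nobody from a group would pass for any group share up to 8.3%, but not for a larger or combined group.

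**What estimation would show instead.** Exact (Clopper-Pearson) 95% intervals at n = 40:

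| Count | Share | 95% CI | Half-width |
|---|---|---|---|
| 0 | 0% | 0 to 8.8% (upper limit 1 − 0.025^(1/40)) | – |
| 10 | 25% | 12.7% to 41.2% | 14.2 points |
| 13 | 32.5% | 18.6% to 49.1% | 15.3 points |
| 20 | 50% | 33.8% to 66.2% | 16.2 points |

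**The case against.** The strongest reply is that no test is planned. The reach analysis is descriptive, so the error rates above belong to a procedure the plan does not contain, and the remedy is close to what is already intended. That stands, and it limits the point. A reader might infer that the plan will run an underpowered test and declare representativeness; the documents do not say so. What remains is that Hypothesis 1a is worded in terms of statistical difference while the analysis section is not, and nothing says which governs the conclusion.

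A reader might also take 85% as the chance of missing the disparity that the Background describes. It is not. The Background's strong wording covers both income contrasts, and that joint skew would be detected 55% to 65% of the time. The 85% applies to the low-income gap alone.

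Nor do the documents support the reading that race is ignored. Aim 1 says demographic characteristics will be examined and demographic data are collected at baseline. What is missing is race in the stated reach analysis. Likewise, the content of MacArthur questions 6 and 7 is not given, so only the Wisconsin comparator is known to be income.

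Finally, this is a pilot meant to inform a later trial, no treatment conclusion depends on Hypothesis 1a, and the Layperson summary describes the current phase as the social-engagement study, which is Study 2. All of this lowers the severity. It does not make non-significance at n = 40 evidence of similarity.

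**Conclusion.** The point holds as one about wording and alignment. Hypothesis 1a cannot be supported by a non-significant result from 40 people without a margin, and it does not match the descriptive analysis, which leaves out race. That conclusion rests on the text and on the logic of testing, not on any income figure.

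The size is illustrative only. It depends on Missouri community shares used as individual proportions, an assumed exact test at two-sided 0.05, and assumed Wisconsin shares. Over assumed low-income shares of 20% to 45%, an 8.3-point shortfall is missed 70% to 85% of the time, so the picture does not turn on one chosen benchmark. Severity is minor given the pilot status, and the remedy is cheap.

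**What to change.** 1. Reword Hypothesis 1a as estimation: report the low-income share and each race share of those enrolled, with exact 95% confidence intervals, beside the Wisconsin figures.
2. Name the source and year of the Wisconsin figures in advance.
3. State that representativeness will not be concluded from a non-significant difference.
4. Add race to the reach analysis in Power and Statistical Analysis.

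The cost is a few sentences and one table from demographic and questionnaire data already planned for collection; no extra participants or visits are needed. The downside is that half-widths of about 14 to 16 points for shares of 25% to 50% may make reach read as inconclusive, which is what 40 people can support.

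A separate wording matter in the same section: Study 2 Aim 2 asks whether social interaction "significantly improves activities of daily living, fall rate and quantity of movement for individuals with PD", while its Hypothesis 2b predicts that the fall-rate improvement will not reach significance. The two should be reconciled; no planned analysis changes.

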### **Study 2**

**SPECIFIC AIM 1:** Determine whether incorporation of social interaction during physical activity significantly improves task adherence and increases task stamina as compared to solo cycling.

**Hypothesis 1a:** Those individuals participating in socially engaged cycling will complete a significantly greater number of cycling sessions than individuals in the solo cycling group.

**Hypothesis 1b:** Individuals in the social cycling group will cycle for longer durations at each session than solo cyclists, despite the long term goal being 30 minutes per session for both groups.

**SPECIFIC AIM 2:** Determine whether incorporation of social interaction during physical activity significantly improves activities of daily living, fall rate and quantity of movement for individuals with PD. The primary variables for this aim are Performance Assessment of Self-care Skills Assessment scores, gait velocity and step count.

**Hypothesis 2a:** Socially engaged exercise will result in significantly greater improvement in measures of instrumented activities of daily living (IADL; as measured by the Performance Assessment of Self-care Skills (PASS) assessment) as compared to solo cycling.

**Hypothesis 2b:** Fall rate will be non-significantly improved with socially engaged cycling but not with solo cycling. Weekly calls will be placed to both groups to record fall rate. Falls data will allow for effect size calculations for future applications.

**Hypothesis 2c:** Overall activity level, as measured by an activity monitor, will increase with socially engaged cycling but not with solo cycling.

**Study Duration:** This study will be conducted over the next 4 years including all data analysis, manuscript and grant proposal submissions.

### **Research Design**

This pilot study will utilize two separate experimental designs to address: 1) the Reach, Effectiveness, Implementation and Maintenance and 2) the optimal delivery method for an in-home exercise intervention program for individuals with PD living in underserved communities. Both studies will utilize paired, randomly assigned groups to explore the given questions. Pairs will be based on disease severity (UPDRS III scores) and age.

Study 1: The proposed pilot study will utilize the RE-AIM framework (Reach, Effectiveness, Adoption, Implementation and Maintenance) to focus on the reach and effectiveness of a 6-month triweekly in-home cycling program and then pilot a health coach model to promote maintenance for the subsequent 3-month period. 40 qualified individuals will be paired based on disease severity (score on subsection III of the UPDRS) and age and randomly assigned to either the cycling group or the normal care control group for 6 months. For those in the cycling group, participants will interact via Skype with study team members during all cycling sessions. This intervention will allow the individuals enrolled to participate in regular exercise and a community activity that promotes social support and engagement. The proposed pilot maintenance model for the 3-month period following the intervention will implement a health coach model with scheduled sessions every other week to discuss goals and motivation while decreasing the total contact time with the participant. Individuals in the normal care control group will crossover and complete the cycling intervention following the initial 6 months.

Study 2: 12 people with PD, living in rural settings or with barriers to travel and who have reported that proximity to community-based exercise is a primary barrier to enrollment will be enrolled in the study. Qualified individuals will be paired based on disease severity (score on subsection III of the UPDRS) and age and randomly assigned to either the social cycling group or solo cycling group for 6 months. Both groups will have an exercise bike delivered to their home, custom fit to their needs and installed in a safe location. Sessions will consist of up to 30 minutes of cycling. Those in the social group will cycling while engaged in social interaction with a research staff member, thus providing a social/community aspect that would not otherwise be present. Those in the solo group will have a target duration and intensity but will exercise without a partner.

### **For both studies**

#### **Participants:**

Inclusion and exclusion criteria is identical for both studies.

Inclusion criteria for all enrolled participants include:

- 1) 45 years of age or older
- 2) diagnosis of idiopathic “definite PD” (Racette, Rundle, Parsian, & Perlmutter, 1999) based upon established criteria (Calne, Snow, & Lee, 1992; Hughes, Daniel, Kilford, & Lees, 1992)
- 3) vision at or corrected to 20/40 or better
- 4) ability to independently ambulate for at least 10 minutes continuously
- 5) no reported vestibular or neurological disease (stroke or muscle disease) beyond their diagnosed PD
- 6) score of greater than or equal to 78 (no evidence of dementia) on the telephone adaptation of the modified mini-mental state exam (Norton et al, 1999) .
- 7) English Speaking

Exclusion criteria for all enrolled participants include:

- 1) contraindication for exercise
- 2) history of muscular or orthopedic diagnosis

- 3) inability to participate in the full duration of the study.
- 4) currently exercising for 20 or more minutes per week.

**Participant Identification and Study Recruitment:** To recruit prospective participants to this study, we will utilize flyers, email, website and Facebook postings, presentations at support group meetings and special events, as well as word of mouth.

Flyers will only be posted after gaining permission at the site in question. To this end, we will contact other research colleagues at the University of Wisconsin, who are also working with elderly individuals and individuals with Parkinson disease (PD), including the Speech & Language Disorders Clinic of the Communication Sciences & Disorders Department and the UW Hospital Movement Disorders Clinic. Additionally, we will work with surrounding rural community hospitals asking them to post and handout the materials for their patients and patients' caregivers. We will also request permission through the UW Health Sports Medicine Fitness Center (UWHSMFC) in Madison, WI to disseminate the flyer to their Parkinson disease fitness classes, Falls Free Living class and similar programs targeted for elderly individuals and those with PD. We will also approach individuals at locations throughout the state where PD support classes and programming for elders is currently taking place. We will also work with the Wisconsin Chapter of the American Parkinson Disease Association, the Wisconsin Institute for Healthy Aging (WIHA), the Community Academic-Aging Research Network (CAARN), the Collaborative Center for Health Equity, and the Aging and Disability Research Centers (ADRC) of Milwaukee and Southwest WI to post notifications on their website and social networking accounts, as well as make presentations at local chapter support groups, events, and fundraisers. Finally, we will utilize the Sensory Motor Integration Laboratory's website and Facebook account to disseminate electronic information about the study.

**Privacy and Confidentiality:** One potential risk of participating in this study is that confidential information about the participants may be accidentally disclosed. If a participant's current diagnosis of PD is not known to others, the potential to cause damage to their psychological well-being as well as to their reputation exists.

To decrease this risk, data will be stored in a double secured location. In a locked filing cabinet (paper data) or on a secure network server.

All data collection sessions will occur in the private setting of the Sensory Motor Integration Lab. While multiple participants may be in the lab for data collections simultaneously, the lab is divided into three separate data collection areas which allows each participant to have maximum privacy.

All data will be coded at the time of data collection. All participants will be assigned an identification number prior to data collection and all documents and files will be named using this ID. All data will be stored on computers which will be kept in the SMIL during data collection and transferred to the School of Education's secure server either via an Ethernet connection or through UW Box. All data analysis will be performed on computers in the SMIL or in the faculty office of the PI. A password is necessary for access to the computers and they all are equipped with automatic log off. Data being moved from one location to another will be moved via UW Box or the School of Education's secure network. Access to these computers are limited to SMIL staff, therefore identification of any subjects or data is unlikely. Coded data will be kept indefinitely.

**Monitoring Software:** Activity tracker and Ride Social accounts will be established with dummy identifiers (SMIL1, SMIL2). The only link that will exist between the individual's identifiers and the accounts will be on the participant code document. Data will be downloaded from the web accounts weekly and logged in the participants data file. The only concern that currently exists is if the individual attempts to reset or create their own account for either tool and discloses their personal information. Individuals will be instructed at the beginning of the study that an account has been made for them and they should not attempt to make a new account.

**Video Data:** All video data will be stored on the School of Education server in a directory designated to the SMIL lab. Only specified lab personnel have access to the network server directory. The server is maintained by the School of Education and is backed-up nightly. Dartfish video analysis software will be used to obscure facial features of participants.

**Contact information:** Each participant will have a sealed folder which contains their emergency contact information including instructions for the local 911 operator and contact information for an identified contact person. The sealed folders marked with the participant names will be kept locked in the PI's research office. These folders are to be unsealed only in the case of an emergency. All folders and their contents will be destroyed once the individual completes the three-month follow-up or if they withdraw from the study.

**Data Sharing:** [name] will be responsible for deciding when/to whom to disseminate coded data, and will work with other researchers if necessary to confirm that they have proper IRB approval/etc., as necessary. Required UW-Madison IRB approval would be obtained prior to the release of any data.

**Substudies:** Two separate studies will occur as part of the larger experiment.

#### Study 1

Examine the reach, effectiveness and maintenance of an in-home, partnered cycling program for underserved individuals with PD.

#### Study 2

Examine the effects of social engagement during in-home exercise on a small sample of individuals with Parkinson Disease (PD). This pilot investigation will directly measure the effect of social support and engagement for rural dwelling individuals with PD.

